8.8 Shipping and Storage

FF-10502-01 vials and FF-10502-01 prepared dosing solution should be stored under refrigerated conditions (2 – 8°C).

8.9 Drug Accountability

The investigator must maintain accurate records of receipt of study drug, dispensing information, and the prompt return or destruction of unused supplies. A drug accountability log will be supplied to each clinical site for purposes of recording study drug dispensation for the study and will be monitored by sponsor personnel. If the site has an electronic study drug accountability form that is in keeping with institutional practice and the form collects the same information as the form supplied by the Sponsor, this form may be substituted for the Sponsor's drug accountability form.

Unused or expired FF-10502-01 will be destroyed per institutional policy.

9 STUDY PROCEDURES

See Schedule of Study Procedures in [APPENDIX D](#). Unless otherwise specified, the study procedures listed in the following subsections apply to all cohorts.

9.1 Screening Procedures

The following evaluation includes standard tests that are to be performed within 28 days prior to the first administration of study treatment to determine patient eligibility.

- Administration of informed consent
- Medical history, physical examination and vital signs
 - In addition to the medical history collected at Screening to determine eligibility, patients will be queried to determine whether they have a history of autoimmune disease or treatment associated with an elevated risk of PML. Specifically, patients will be queried about a history of:
 - Systemic lupus erythematosus
 - Rheumatoid arthritis
 - Sjogren's syndrome
 - Dermatomyositis or polymyositis
 - Idiopathic thrombocytopenic purpura
 - Vasculitis (cryoglobulenic, Giant cell etc)
 - Multiple sclerosis and treatment with an integrin inhibitor such as natalizumab
 - Hematologic malignancy such as lymphoma and treatment with rituximab or anti-CD20 therapy

Medical history pertaining to any autoimmune disease or treatment associated with an elevated risk of PML will be entered in the clinical database but does not constitute eligibility criteria.

- ECOG Performance Status
- Height and weight
- The following lab tests: (See [Table 3](#) for a list of lab tests)
 - Hematology
 - Coagulation parameters
 - Serum chemistry
 - Urinalysis
- β -HCG for WCBP within 14 days prior to the first dose of FF-10502-01
- 12-lead ECG
- Patients may consent to an optional tumor biopsy during screening. (Refer to [Section 10.1.13](#))
- Review of concomitant medications
- Disease-specific assessment (CT, MRI scans)

9.2 Treatment Cycles

9.2.1 Requirements During Treatment Cycle 1

9.2.1.1 Cycle 1, Day 1

- Abbreviated physical examination
- Vital signs
- ECOG Performance Status
- Weight
- The following lab tests: (See [Table 3](#) for a list of lab tests)
 - Hematology, if not performed within the previous 72 hours. Note: In addition to total lymphocyte counts, T cell (CD4 and CD8) and B cell counts will be obtained.
 - Serum chemistry, if not performed within the previous 72 hours
 - Urinalysis, if not performed within the previous 72 hours
- Patients who have not done so at screening may consent to an optional tumor biopsy during Cycle 1. (Refer to [Section 10.1.13](#))
- Review of concomitant medications
- Assessment of AEs
- Administration of FF-10502-01 over a 1-hour period
- Peripheral blood collection in EDTA for PK assessments, pre-dose, immediately following cessation of infusion (within 15 minutes), between 1-2 hours post-infusion, and between 4-6 hours post-infusion
- Peripheral blood collection in sodium heparin for pharmacodynamic assessment, pre-dose

9.2.1.2 Cycle 1, Day 8 (± 1 day)

- Vital signs
- The following lab tests: (See [Table 3](#) for a list of lab tests)
 - Hematology
 - Serum chemistry
- Patients who have not done so at screening may consent to an optional tumor biopsy during Cycle 1. (Refer to [Section 10.1.13](#))
- Review of concomitant medications
- Assessment of AEs
- Administration of FF-10502-01 over a 1-hour period
- **Cohort 13 only:** Peripheral blood collection in EDTA for PK assessments, pre-dose, immediately following cessation of infusion (within 15 minutes), between 1-2 hours post-infusion, and between 4-6 hours post-infusion

- Peripheral blood collection in sodium heparin for pharmacodynamic assessment, pre-dose

9.2.1.3 Cycle 1, Day 15 (± 1 day)

- Vital signs
- The following lab tests: (See [Table 3](#) for a list of lab tests)
 - Hematology
 - Serum chemistry
- Patients who have not done so at screening may consent to an optional tumor biopsy during Cycle 1. (Refer to [Section 10.1.13](#))
- Review of concomitant medications
- Assessment of AEs
- **Cohorts 1 to 12 only:** Administration of FF-10502-01 over a 1-hour period
- **Cohorts 1 to 12 only:** Peripheral blood collection in EDTA for PK assessments, pre-dose, immediately following cessation of infusion (within 15 minutes), between 1-2 hours post-infusion, and between 4-6 hours post-infusion
- Peripheral blood collection in sodium heparin for pharmacodynamic assessment, pre-dose (Cohorts 1 to 12) or any time during visit (Cohort 13)

9.2.1.4 Cycle 1, Day 22 (± 1 day) [**Cohorts 1 to 12 only**]

- Vital signs
- The following lab tests: (See [Table 3](#) for a list of lab tests)
 - Hematology
 - Serum chemistry
- Patients who have not done so at screening may consent to an optional tumor biopsy during Cycle 1. (Refer to [Section 10.1.13](#))
- Review of concomitant medications
- Assessment of AEs
- Peripheral blood collection in sodium heparin for pharmacodynamic assessment during visit

9.2.2 Requirements During Treatment Cycles After Cycle 1 (Cycles 2, 3, 4, etc)

9.2.2.1 Day 1 of Each Cycle (± 2 days)

- Abbreviated physical examination
- Vital signs
- ECOG Performance Status
- Weight
- The following lab tests (within 3 days of each cycle – see [Table 3](#) for a list of lab tests):

- Hematology. Note: In addition to total lymphocyte counts, T cell (CD4 and CD8) and B cell counts will be obtained.
- Serum chemistry
- Urinalysis
- Review of concomitant medications
- Assessment of AEs
- Administration of FF-10502-01 over a 1-hour period

9.2.2.2 *Day 8 of Each Cycle (±2 days)*

- The following lab tests (see [Table 3](#) for a list of lab tests):
 - Hematology
- Review of concomitant medications
- Assessment of AEs
- Administration of FF-10502-01 over a 1-hour period

9.2.2.3 *Day 15 of Each Cycle (±2 days) [Cohorts 1 to 12 only]*

- The following lab tests (see [Table 3](#) for a list of lab tests):
 - Hematology
- Review of concomitant medications
- Assessment of AEs
- Administration of FF-10502-01 over a 1-hour period

9.2.2.4 *End of Cycle 2 and Every 2 Cycles Thereafter (±3 days)*

- Disease-specific assessment (CT, MRI scans)
- Review of concomitant medications
- Assessment of AEs

9.3 **At Relapse or Progression of Disease**

- Disease-specific assessment (CT, MRI scans)
- Review of concomitant medications
- Assessment of AEs

9.4 **End of Treatment (28 days, ± 5 days, from the last dose of Study Drug)**

- Physical examination
- Vital signs
- ECOG Performance Status
- Weight
- The following lab tests: (See [Table 3](#) for a list of lab tests)

- Hematology. Note: In addition to total lymphocyte counts, T (CD4 and CD8) and B cell counts will be obtained at end of treatment.
- Serum chemistry
- Urinalysis
- 12-lead ECG
- Review of concomitant medications
- Assessment of AEs

9.5 Long-term Follow-up

Long-term follow-up will consist of a clinic visit or telephone call every 3 months until death or patient's refusal to participate to assess survival.

10 DESCRIPTION OF ASSESSMENTS

10.1 Safety Assessments

10.1.1 Adverse Event Definition

An adverse event (AE) includes any noxious, pathological, or unintended change in anatomical, physiological, or metabolic functions as indicated by physical signs, symptoms, and/or laboratory changes occurring whether or not temporally associated with study drug administration and whether or not considered related to study drug. This definition includes an exacerbation of pre-existing medical conditions or events, intercurrent illnesses, hypersensitivity reactions, drug interactions, or clinically significant laboratory findings.

An AE does not include the following:

- Medical or surgical procedures, eg, tooth extraction, transfusion, surgery (The medical condition that leads to the procedure is to be recorded as an AE.)
- Pre-existing conditions or procedures present or detected at the start of the study that do not worsen
- Hospitalization for elective surgeries or for other situations in which an untoward medical event has not occurred
- Abnormal laboratory value, unless it is clinically significant
- Overdose of study drug or concomitant medication unaccompanied by signs/symptoms (If sign/symptoms occur, the final diagnosis should be recorded as an AE.)
- Pregnancy by itself, unless a complication occurs during pregnancy leading to hospitalization; in this case (The medical condition that leads to the hospitalization is to be recorded as the AE.)
- A significant worsening of the disease under investigation which is captured as an efficacy parameter in this study and, thus, is not to be recorded as an AE.

10.1.2 Serious Adverse Event

A serious adverse event (SAE) is defined as an adverse event that results in any of the following outcomes:

- Death
- Life-threatening, ie, immediate risk of death from the event as it occurred; (This does not include an adverse event that, had it occurred in a more serious form, might have caused death.)
- Persistent or substantial disability/incapacitation
- Results in or prolongs an existing inpatient hospitalization
- Congenital anomaly/birth defect

Important medical events that may not result in death, be life-threatening, or require hospitalization may be considered serious when, based on medical judgment, they may jeopardize the patient or may require medical or surgical intervention to prevent one of the outcomes listed in this definition.

10.1.3 Unexpected Adverse Event

An AE or suspected adverse reaction is considered "unexpected" if it is not listed in the Investigator's Brochure or is not listed at the specificity or severity that has been observed; or, is not consistent with the risk information described in the protocol or elsewhere. For example, under this definition, hepatic necrosis would be unexpected (by virtue of greater severity) if the Investigator's Brochure referred only to elevated hepatic enzymes or hepatitis. Similarly, cerebral thromboembolism and cerebral vasculitis would be unexpected (by virtue of greater specificity) if the Investigator's Brochure listed only cerebral vascular accidents.

"Unexpected," as used in this definition, also refers to AEs or suspected adverse reactions that are mentioned in the Investigator's Brochure as occurring with a class of drugs or as anticipated from the pharmacological properties of the investigational therapy, but are not specifically mentioned as occurring with the investigational therapy.

10.1.4 Adverse Event Reporting Period

The adverse event reporting period begins from the date of the first dose of study drug to 28 days following the last dose of study drug.

10.1.5 Recording of Adverse Events

Each AE should be recorded in standard medical terminology on the AE CRF module. Whenever possible, the AE should be evaluated and reported as a diagnosis rather than as individual signs or symptoms. For example, cough, runny nose, sneezing, sore throat, and head congestion should be reported as 'upper respiratory infection'. If a definitive diagnosis is not possible, the individual signs and symptoms should be recorded. Dates of start (onset) and stop (recovery), action taken, and outcome will be recorded in the AE CRF module.

All clinically significant abnormal changes in laboratory parameters will be recorded as an AE on the AE module, with the following exceptions: clinically significant abnormal laboratory changes determined to be related to the study condition and concomitant conditions, eg, diabetes, of which the investigator was previously aware and that have not worsened.

The investigator will evaluate all AEs with regard to maximum intensity and relationship to study drug, as follows.

10.1.5.1 *Maximum Intensity*

Maximum intensity should be assigned using one of the severity grades as outlined in the National Cancer Institute Common Terminology Criteria for Adverse Events (NCI CTCAE v4.03); if the AE is not specifically listed in CTCAE v4.03, use the following grades:

- Grade 1: mild
- Grade 2: moderate
- Grade 3: severe
- Grade 4: life-threatening
- Grade 5: death

10.1.5.2 *Relationship to Study Drug*

The degree of certainty with which an AE is attributed to study drug (or alternative causes, eg, natural history of the underlying diseases, concomitant therapy, etc) will be determined by how well the event can be understood in terms of known pharmacology of the study drug and/or

reactions of similar nature previously observed with study drug. Each AE will be assigned one of the following five categories:

- Not related: There is not a temporal relationship to the study drug (eg, too early, too late), or there is a reasonable causal relationship to another drug, concurrent illness, or circumstance.
- Unlikely related: There is a temporal relationship to study drug, but there is not a reasonable causal relationship between the time of study drug administration and the AE (ie, it is doubtful the AE is related to the study drug); could be reasonably explained by other factors, including underlying disease, complications, concomitant drugs, or concurrent treatment.
- Possibly related: There is a reasonable temporal sequence from time of study drug administration (eg, occurred in a time frame relevant to study drug dose); or for which the possibility of the study drug being the causative factor (eg, existence of similar reports attributed to the study drug; reactions attributable to the pharmacological effect) could not be excluded, although other factors such as underlying disease, complications, concomitant drugs, or concurrent treatment are presumable.
- Probably related: There is a reasonable temporal sequence from time of study drug administration; and for which the possibility of factors other than the study drug administration, such as underlying disease, complications, concomitant drugs, or concurrent treatment, could not be excluded as the cause.
- Definitely related: Follows a clear temporal sequence from time of study drug administration; could not be possibly explained by the known characteristics of the patient's clinical state, environmental or toxic factors, or other modes of therapy administered to the patient; follows a response pattern known to be associated with study drug administration.

10.1.6 Adverse Event Reporting

Each AE is to be reported by the investigator as serious or non-serious according to the definitions in Section 10.1.2 above. This classification determines the regulatory reporting procedures to be followed as described in Table 2.

Table 2. Reporting Guidelines for Adverse Events

Gravity of AE	Reporting Time to FPHU/Westat	Type of Report
Serious	Within 24 hours after the site becomes aware of the event	Initial SAE Report
Non-Serious	Per AE CRF module	Completed AE CRF Module

Any SAE, regardless of relationship to investigational therapy that occurs within 28 days following the last dose of study drug must be reported to the Medical Monitor within 24 hours after the site becomes aware of the event. The investigator is encouraged to discuss with the Medical Monitor any adverse experiences for which the issue of reportability is unclear or questioned. The initial report should be followed by submission of a more detailed SAE Report when follow-up information is available.

If the SAE occurs more than 28 days after the last dose of study drug, SAEs should be reported only if considered related to FF-10502-01. In the event of patient death, the reason for death should be recorded as the SAE, with 'death' recorded as the outcome on the SAE CRF module.

The SAE also will be recorded as an AE on the AE CRF module. Note: the SAE Report is different from the AE CRF. In areas of both forms where the same data are reported, the forms will be completed in a consistent manner. For example, the same term should be used for the AE on both forms, with the same start and stop dates, action taken, outcome, etc. A checkbox on the AE CRF module for whether the AE resulted in an SAE, will link the two types of report for a given event.

An SAE Report should be prepared with as much available information concerning the event as possible so that a written report can be filed with the appropriate regulatory authorities. If causality cannot be determined definitively at the time of the SAE occurrence, it is important to notify FPHU/Westat within the timeline stated above, and to attribute the relationship as 'Not Assessable' (only applicable for the initial SAE Report). When new significant information is obtained and the outcome and attribution of the event is known, the investigator will communicate this in a follow-up SAE Report. This relevant information will be provided in a timely manner to allow reporting to regulatory authorities within the required reporting period. Any SAE follow-up information requested by FPHU/Westat should be provided in a timely manner.

As necessary, the SAE Report should be accompanied by relevant pages from the CRFs, eg, medical history, AEs, concomitant medications. Additional information may be requested by FPHU/Westat in an expedited manner to ensure that the initial reporting of the SAE made to the regulatory authorities complies with the required time frame. FPHU/Westat may be required to collect and report additional information to the regulatory authorities in a follow-up report, containing a final evaluation of the event, including copies of hospital reports, autopsy reports, or other relevant information.

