7.3 Discontinuation of Patients

7.3.1 Procedures for Withdrawal

Any patient may be removed from study for the following reasons:

- Patient withdrawal of consent
- Patient noncompliance

- An increasing or unexpected pattern of unacceptable toxicity
- Disease progression
- Investigator judgment when the well-being and best interest of the patient is compromised

Patients experiencing unacceptable toxicity should be removed from the study once complete resolution of toxicity has been documented. Individual patients may be discontinued from the study by the investigator or sponsor at any time if either determines that it is not in the best interest of the patient to continue.

Any patient who becomes pregnant during the study must be discontinued from study treatment immediately but should be followed through delivery or termination of the pregnancy. Patients should also notify the investigator if they become pregnant within 28 days following the last dose of study drug. FPHU/Westat also must be notified if a patient becomes pregnant on study.

If a patient is discontinued from the study before completing the specified duration of treatment, they should be encouraged to complete the end-of-study assessments and to agree to report any serious adverse events for 28 days following the last dose of study drug. The date the patient is withdrawn and the primary reason for discontinuation will be recorded on the case report form (CRF).

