8.4.3 Study Stopping Criteria

The occurrence of any new cases of PML will prompt FPHU to immediately halt any recruitment and consult with the FDA as the details of the new case are acquired. Details include confirmation of diagnosis per established criteria, history of past medication associated with PML and other items of interest. Treatment of other patients on study may be withdrawn upon consultation with the FDA and investigators.

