APPENDIX D. Schedule of Study Procedures

Table 6: Schedule of Procedures for Cohorts 1-12

Study Activity	Screening ¹	Treatment Cycle 1				Treatment Cycles After 1				Progression/ Relapse	EOT ²	Long-term FU ³
		D1	D8 ⁴	D15 ⁴	D22 ⁴	D1 ⁵	D8	D15	End of C2 ^{6,7}			
Signed ICD	X											
Medical history	X											
Physical examination	X	X ⁸				X ⁸					X	
Vital signs	X	X	X	X	X	X					X	
ECOG PS	X	X				X					X	
Height	X											
Weight	X	X				X					X	
Hematology ⁹	X	X	X	X	X	X	X	X			X	
CD4, CD8, and B-cell counts		X				X					X	
Coagulation	X											
Serum chemistry ¹⁰	X	X	X	X	X	X					X	
Urinalysis ¹¹	X	X				X					X	
β-hCG (WCBP)	X											
12-lead ECG	X										X	
Concomitant medications	X	Continuous										
AE assessment		Continuous										
Disease response assessment ¹²	X								X	X		
Blood for PK assessment ¹³		X		X								
Blood for PD assessment ¹⁴		X	X	X	X							
FF-10502-01 administration ¹⁵		X	X	X		X	X	X				

Study Activity	Screening ¹	Treatment Cycle 1				Treatment Cycles After 1				Progression/ Relapse	EOT ²	Long-term FU ³
		D1	D8 ⁴	D15 ⁴	D22 ⁴	D1 ⁵	D8	D15	End of C2 ^{6,7}			
Survival assessment		X	X	X	X	X	X	X	X	X	X	X
Tumor biopsy		X ¹⁶										

Abbreviations: AE, adverse event; β -hCG, beta human chorionic gonadotropin; C, cycle; CT, computed tomography; D, day; EDTA, ethylenediaminetetraacetic acid; ECG, electrocardiogram; ECOG PS, Eastern Cooperative Oncology Group Performance Status; EOT, end of treatment; FU, follow-up; ICD, informed consent documentation; MRI, magnetic resonance imaging; PD, pharmacodynamics; PK, pharmacokinetics; WBCP, women of childbearing potential.

¹ Screening to be performed within 28 days before Cycle 1, Day 1.

² End of Treatment visit should be 28 days from last dose of study drug (\pm 5 days).

³ Long-term follow-up consists of clinic visits or telephone calls every 3 months to assess survival status.

⁴ Day 8, 15, or 22 \pm 1 day.

⁵ Day 1 (window \pm 2 days).

⁶ Day 28 \pm 3 days.

⁷ And every 2 cycles thereafter.

⁸ Abbreviated physical exam.

⁹ Hematology collected at Screening, Cycle 1 Day 1 (only if not performed in the previous 72 hours), Days 8, 15 and 22, Day 1 of each subsequent cycle (within 3 days of Day 1 of each subsequent cycle), Day 8 and 15 of each cycle (pre-dose) and End of Treatment. See [Table 3](#) for tests to be conducted at each time point.

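### Any new PML case halts recruitment, but a non-fatal case starting more than 28 days after the last dose and judged not related has no mandatory route to the sponsor

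*Protocol*

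**What the plan says.** Protocol Section 8.4.3 holds one study stopping criterion: "The occurrence of any new cases of PML will prompt FPHU to immediately halt any recruitment and consult with the FDA". The sponsor acts while details are still coming in. Those details include confirmation of the diagnosis and earlier drugs linked to PML. The section does not restrict the trigger by time since last dose or by attribution.

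The reporting rules are narrower:

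- **Section 10.1.4.** The AE reporting period "begins from the date of the first dose of study drug to 28 days following the last dose of study drug". SAP Section 3.4.2 presents AEs over the same window.
- **Section 10.1.6.** Up to 28 days after the last dose, every SAE goes to the Medical Monitor within 24 hours of site awareness, whatever its relationship to the drug. After that, "SAEs should be reported only if considered related to FF-10502-01".
- **Section 7.3.1.** Patients who stop early are encouraged "to agree to report any serious adverse events for 28 days following the last dose of study drug".
- **Section 9.5.** Long-term contact takes place "every 3 months until death or patient's refusal to participate to assess survival". Footnote 3 of Tables 6 and 7 in Appendix D agrees: "Long-term follow-up consists of clinic visits or telephone calls every 3 months to assess survival status".

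PML otherwise appears in the abbreviation list and in Section 9.1, where a history of PML-associated disease or treatment "will be entered in the clinical database but does not constitute eligibility criteria".

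**The concern.** The stopping rule and the reporting rule treat attribution differently. Section 8.4.3 stops recruitment first and examines alternative causes afterwards. After day 28, Section 10.1.6 lets the site's view of alternative causes decide whether the sponsor hears of the case at all.

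The wording of 'not related' in Section 10.1.5.2 can fit a late case. It covers events with no temporal relationship ("eg, too early, too late), or there is a reasonable causal relationship to another drug") and also those explained by a concurrent illness or other circumstance. A patient with earlier natalizumab or anti-CD20 treatment may enrol under Section 9.1 and would bring a ready alternative cause. So a prior drug, which Section 8.4.3 treats as something to look into once the sponsor is already acting, could become the reason for not reporting.

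The stake is patient safety. Recruitment could continue after a case that the protocol says should stop it.

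**Working it through.** No arithmetic applies: the point rests on reporting rules, and the documents give no PML incidence. The check follows one case through every route in the text by which it could reach the sponsor. The case is serious, non-fatal PML with onset more than 28 days after the last dose, judged not related by the site, while recruitment is open.

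| Route | Where | Does it oblige the site to tell the sponsor? |
|---|---|---|
| AE form | 10.1.4 | No; the period has ended |
| SAE report | 10.1.6 | No; after day 28, related events only |
| 24-hour line for serious events | Table 2 in 10.1.6 | No; it shows no time limit, but the text below it adds the 28-day and relatedness limits |
| Cause of death entered as the SAE | 10.1.6 | No; the case is non-fatal |
| Direction to notify when causality cannot be settled | 10.1.6 | No; causality has been judged |
| Discussion with the Medical Monitor | 10.1.6 | No; encouraged, and only where reportability is in doubt |
| Follow-up of existing events | 10.1.7 | No; onset was after day 28 |
| AE assessment at two-cycle disease assessments and at progression | 9.2.2.4, 9.3 | No formal duty, but the case may surface |
| End of Treatment visit, 28 ± 5 days after last dose (so up to day 33) | 9.4 | No formal duty after day 28, but the case may surface |
| 3-monthly contact | 9.5, Appendix D | No; survival only |
| Monthly safety teleconference | 10.1.8 | No; reviews AE/SAE profiles without a new site duty |
| Safety Review Committee, at least quarterly | 6.1 | No; investigators sit on it and may mention a case, but need not |
| Prompt notice of unanticipated problems | Appendix F | Mandatory, but goes to the IRB |
| Final report | Appendix F | After completion or termination; to the sponsor only if required |

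No mandatory route to the sponsor remains for this case. The same holds for a case rated 'unlikely related' if the site treats that category as not related.

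The timing is possible. Phase 1 accrual took about 24 months, Phase 2a accrual is planned for up to 21 months (Section 6.3), and follow-up runs until death or refusal (Section 9.5). Some patients can be beyond day 28 while others are still being enrolled.

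Changing one feature of the case shows where the gap ends:

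- **Drug cannot be excluded.** Section 10.1.5.2 makes this 'possibly related', even where other causes are presumable. The case is reportable.
- **Causality undetermined.** Section 10.1.6 directs the site to notify within the 24-hour timeline as 'Not Assessable' and attaches no 28-day limit to that sentence.
- **Fatal case.** Probably captured through the cause of death.
- **Onset by day 28, diagnosed later.** Captured by follow-up under Section 10.1.7.

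**The case against.** The strongest reply has three parts.

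First, a site is unlikely to rate PML definitely 'not related' in this trial. The protocol itself contains a PML stopping rule and PML risk screening, attribution takes account of similar reactions seen before with the drug, and a site with any doubt is directed to notify. This stands and makes the gap small. It does not close it, because the wording of 'not related' still fits a late case with another cause, and the choice is the site's.

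Second, Section 8.4.3 says what the sponsor does once it knows of a case. It does not promise surveillance beyond the reporting period, and related-only reporting after day 28 is a deliberate choice. That is a fair reading of the general SAE rule. It sits poorly with a trigger worded to cover any new case and acted on before alternative causes have been examined.

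Third, the missing instruction may exist elsewhere. Section 4.5, the Safety Review Committee Charter and the Investigator's Brochure with its supplement were not available. This stands, and the conclusion is limited accordingly. Sections 10.1.4 to 10.1.8 are complete and contain neither a PML exception nor a pointer to one.

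Two stronger readings are tempting. A reader might infer that the sponsor would hear of no PML after day 28. The documents do not support that: related, possibly related and undetermined cases are reportable, fatal ones probably are, and AE assessment can continue at disease assessments and at progression. A reader might also infer from the word 'new' in Section 8.4.3 that an earlier case was attributed to the drug. The available text does not say so.

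**Conclusion.** The point holds in a narrow form. By following Section 10.1.6 as written, a site could leave unreported a case that Section 8.4.3 says should halt recruitment.

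Failure needs five things together: onset more than 28 days after the last dose, recruitment still open, a definite 'not related' judgement, a non-fatal course, and no informal mention at an assessment or safety review. That should be rare, and no rate or delay can be derived from the documents. No endpoint, sample size or decision boundary changes.

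The conclusion assumes that no unavailable document already requires PML to be reported outside the 28-day rule, so confidence is moderate. It is a cheap safety improvement and does not call the design into question.

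**What to change.** In Sections 10.1.4 and 10.1.6, add that any diagnosis of PML, or PML under active diagnostic work-up as the leading diagnosis, is reported to the sponsor within 24 hours of site awareness, at any time after the first dose and regardless of attribution. In Section 8.4.3, state whether a case still under work-up triggers the halt or only prompt sponsor review. If the Charter or the Investigator's Brochure already holds such a reporting rule, a cross-reference in Section 10.1.6 would meet the reporting part.

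A question at the 3-monthly contact is optional and not needed for the fix. If added, it should name PML and not ask about any new neurological diagnosis. Section 7.2 allows patients with stable brain metastases, so a broad question would pick up their disease.

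The cost is a short amendment with IRB approval before implementation (Section 12.4), a few extra expedited reports, and a small CRF change if the optional question is used. There is also a small chance of a temporary recruitment halt on a case later not confirmed, because Section 8.4.3 acts before confirmation. Limiting reports to PML as the leading diagnosis, and settling in Section 8.4.3 how work-up cases are handled, keeps that chance low.
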